5 STUDY TREATMENT

5.1 Overview of the Study Drugs

5.1.1 Access to the drugs

The study drugs are uniformly packaged, tested, and provided by the sponsor (see corresponding Certificate of Analysis).

5.1.2 Drug information

Investigational drug: SHR-1210 for injection

Manufacturer: Suzhou Suncadia Biopharmaceuticals Co., Ltd.

Dosage form: lyophilized powder.

Strength: 200 mg (proposed) in 20-mL vials.

Batch No.: see Certificate of Analysis

Route of administration: intravenous injection.

Shelf life: 2 years (tentative) from the date of manufacture.

Storage conditions: sealed, away from light, stored at 2-8 °C in refrigerator. Do not freeze.

Apatinib Mesylate Tablets

Manufacturer: Jiangsu Hengrui Pharmaceuticals Co., Ltd.

Dosage form: tablet.

Strength: 250 mg/tablet; 375 mg/tablet

Batch No.: see Certificate of Analysis

Route of administration: oral administration after meals (best to take the two drugs at the same time each day).

Shelf life: 2 years.

Storage conditions: away from light, sealed, stored below 25 °C.

Capecitabine Tablet

Manufacturer: Jiangsu Hengrui Pharmaceuticals Co., Ltd.

Dosage form: tablet.

Strength: 0.5 g/tablet; 0.15 g/tablet.

Batch No.: see Certificate of Analysis

Route of administration: oral administration after meals.

Shelf life: 24 months.

Storage conditions: kept in a cool and dry place.

Oxaliplatin for Injection

Manufacturer: Jiangsu Hengrui Pharmaceuticals Co., Ltd.

Dosage form: injection.

Strength: 50 mg/bottle or 100 mg/bottle.

Batch No.: see Certificate of Analysis

Route of administration: intravenous infusion.

Shelf life: 24 months.

Storage conditions: sealed and stored below 25 °C.

5.1.3 Drug storage and management

The investigator or authorized personnel (such as a pharmacist) is responsible for ensuring that all study drugs are stored in a safe zone with appropriate storage conditions and controlled access, and that the storage is in compliance with regulatory requirements.

The study drugs should be stored in their original containers according to the storage conditions in section 5.1.2, and the storage conditions are consistent with the label. For inconsistencies between the storage conditions on the label with those in other materials (e.g., Investigator's Brochure), the storage conditions on the label should be followed.

The study center shall record the daily maximum and minimum temperature of all storage zones (such as freezer, refrigerator, or room temperature). Documentation should begin with the receipt of the study drug until the last subject completes the last visit. Even if a continuous monitoring system is employed, a written log must be kept to ensure a correct record of storage temperature. The temperature monitoring and storage devices (such as refrigerator) should be regularly inspected to ensure proper operation.

Any deviations related to the labeled conditions on the product should be immediately reported upon discovery. The study center shall take active measures to restore the study drugs under the storage conditions described on the label, and the temperature deviation and the measures taken shall be reported to the sponsor.

Study drugs that are affected by temperature deviations must be temporarily quarantined until approved by the sponsor for further use, and such case is not considered a protocol deviation. The use of affected study drugs without the approval of the sponsor is considered a protocol deviation. The sponsor will provide a detailed procedure on reporting temperature deviations to the study center.

For subjects who take the medications at home, the staff at the study center will provide guidance for the subjects on the proper method of drug storage as the storage conditions.

The study drugs are not allowed to be used in treatments outside of this study.

5.1.4 Preparation of study drugs

The study drugs should be prepared by qualified or experienced study staff (such as study nurse) according to the drug brochures or package insert of marketed drugs.

SHR-1210 does not contain preservatives, and must be prepared using aseptic technique. Refer to the brochure for drug preparation.

Other study drugs (apatinib mesylate, capecitabine and oxaliplatin) have already been marketed and should be prepared according to the package inserts.

5.1.5 Administration of study drugs

SHR-1210

SHR-1210, intravenous infusion at a fixed dose of 200 mg over 30 min (the total infusion time should be no less than 20 min and no more than 60 minutes, including rinsing period), once every 3 weeks.

Apatinib Mesylate Tablets

375 mg, administered orally once daily. Administered with warm water approximately half an hour after meals (administration time should be the same in each day whenever possible).

Capecitabine

1000 mg/m², administered orally twice daily 30 min after meals (once in the morning and once in the evening; with a total daily dose of 2000 mg/m²). Two weeks of treatment is followed by 1 week of rest period (i.e., drug administration from Day 1 to Day 14, and drug interruption from Day 15 to Day 21) in 3 week cycle.

Oxaliplatin

130 mg/m², intravenous infusion with 250-500 mL of 5% glucose solution, given over 2-6 h; administered on Day 1 of each treatment cycle, once every 3 weeks.

SHR-1210 will be administered intravenously followed by oxaliplatin at least 30 min interval on Day 1 of each cycle.

Study Treatment	Drug	Treatment Cycle (21 days)	
Cohort 1	SHR-1210 200 mg	Day 1	
	Capecitabine 1000 mg/m ²	Day 1-Day 14	4-6 cycles
	Oxaliplatin 130 mg/m ²	Day 1	
	SHR-1210 200 mg	Day 1	
	Apatinib 375 mg	Day 1-Day 21	
Cohort 2	SHR-1210 200 mg	Day 1	
	Apatinib 375 mg	Day 1-Day 21	

Table 6. Administration plan of the study drugs

5.2 Dose Modification of Study Drugs

5.2.1 Dose modification of SHR-1210

Dose increases and reductions of SHR-1210 are not permitted. If SHR-1210 treatment is interrupted due to a toxicity, the subject may resume the treatment at the original dose after the toxicity is resolved. AEs related to SHR-1210 may be immune toxicities, and may occur shortly after the first dose or several months after the last dose. If the conditions listed in [Table 7](#) occur, the use of SHR-1210 should be interrupted. During the study, the investigator must consult with the sponsor if the investigator considers that an adjustment listed in [Table 7](#) is inappropriate based on the benefit-to-risk ratio of subjects or that SHR-1210 treatment should be interrupted or resumed due to a condition not listed in the table.

Table 7. Dose modification criteria for SHR-1210 due to immune-related toxicity

SHR-1210-Related Toxicity	Grade for Interruption	Resumption	Discontinuation
Diarrhea/Colitis	Grade 2-3	Recovered to Grade 0-1	Toxicity has not resolved by 12 weeks after the last dose, or the corticosteroid dose cannot be reduced to prednisone 10 mg/day (or equivalent) or lower within 12 weeks after the last dose.
	Grade 4	Discontinuation	Discontinuation
AST/ALT or Bilirubin Increased	Grade 2	Recovered to Grade 0-1	Toxicity has not resolved by 12 weeks after the last dose, or the corticosteroid dose cannot be reduced to prednisone 10 mg/day (or equivalent) or lower within 12 weeks after the last dose.
	Grade 3-4	Discontinuation ^a	Discontinuation
Type 1 Diabetes Mellitus (new onset) or Hyperglycemia with Signs of β-cell Failure	Grade 3-4 or new-onset type 1 diabetes	SHR-1210 treatment may only be resumed after the clinical and metabolic conditions of the subject are stabilized.	
Hyperthyroidism	Grade 3	Toxicity reduced to Grade 0-1	Toxicity has not resolved by 12 weeks after the last dose, or the corticosteroid dose cannot be reduced to prednisone 10 mg/day (or equivalent) or lower within 12 weeks after the last dose.
	Grade 4	Discontinuation	Discontinuation
Hypothyroidism	Grade 2-4	Study treatment can be continued after starting thyroxine replacement therapy	

SHR-1210-Related Toxicity	Grade for Interruption	Resumption	Discontinuation
Pneumonia	Grade 2	Toxicity reduced to Grade 0-1	Toxicity has not resolved by 12 weeks after the last dose, or the corticosteroid dose cannot be reduced to prednisone 10 mg/day (or equivalent) or lower within 12 weeks after the last dose.
	Grade 3-4	Discontinuation	Discontinuation
Immune-Related Hypophysitis	Grade 2-3	The SHR-1210 treatment may continue after the toxicity reduces to Grade 0-1 and the hormone replacement therapy starts.	Toxicity has not resolved by 12 weeks after the last dose, or the corticosteroid dose cannot be reduced to prednisone 10 mg/day (or equivalent) or lower within 12 weeks after the last dose.
	Grade 4	Discontinuation	Discontinuation
Renal Failure or Nephritis	Grade 2	Toxicity reduced to Grade 0-1	Toxicity has not resolved by 12 weeks after the last dose, or the corticosteroid dose cannot be reduced to prednisone 10 mg/day (or equivalent) or lower within 12 weeks after the last dose.
	Grade 3-4	Discontinuation	Discontinuation
Infusion reactions	Grade 2 ^b	Symptoms disappeared	Discontinue the drugs if the symptoms recur after adequate premedication.
	Grade 3-4	Discontinuation	Discontinuation
Other T-related toxicities ^c	Grade 3	Toxicity reduced to Grade 0-1	Toxicity has not resolved by 12 weeks after the last dose, or the corticosteroid dose cannot be reduced to prednisone 10 mg/day (or equivalent) or lower within 12 weeks after the last dose.
	Grade 4	Discontinuation	Discontinuation

Treatment should be discontinued if any grade ≥ 3 treatment-related AE recurs (grade ≥ 2 pneumonia) or any life-threatening event recurs.

- a) For subjects with liver metastasis and grade 2 AST or ALT increased at baseline, if the AST or ALT increased $\geq 50\%$ from baseline persists for at least 1 week, the treatment shall be discontinued.
- b) If the symptoms resolve within 1 hour after dechallenge, and the infusion can be resumed at 50% of the initial infusion rate. Otherwise, the treatment can only be resumed until symptoms are fully resolved. Premedication is required prior to the next dose. Refer to section 5.6.2 "Recommendations on infusion reaction management" for further management.

- c) For subjects with intolerable or persistent grade 2 treatment-related AEs, the investigator may consider interrupting SHR-1210 treatment if appropriate, and the treatment should be discontinued if toxicity fails to decrease to Grade 0-1 within 12 weeks after the last dose.

5.2.2 Dose modification of capecitabine and oxaliplatin

For subjects receiving SHR-1210 combined with capecitabine and oxaliplatin (XELOX regimen), dose modification can be made based on toxicities.

For non-severe or non-fatal toxicities (eg., alopecia, appetite change and nail discoloration), dose modification may not be necessary as judged by the investigator.

Dose modification caused by toxicities of a single drug in the combination therapy will not affect the usage of other drugs according to the plan.

This is because the capecitabine- and/or oxaliplatin-related toxicities cannot resolve within one same treatment cycle. The administration of capecitabine and/or oxaliplatin can be delayed for no more than 6 weeks. If the toxicities still do not resolve by 6 weeks, the capecitabine and/or oxaliplatin treatment will be discontinued, unless the investigator considers that the subjects will benefit from the continuing treatment of the capecitabine and/or oxaliplatin.

- Dose modification of capecitabine

Toxicities caused by capecitabine can be managed by symptomatic treatment and/or interruption or dose reduction. The recommended dose modification criteria for capecitabine are shown in [Table 8](#). The dose cannot be increased again after the reduction.

Grading of Adverse Drug Reactions	Modification During Treatment	Dose Modification in the Next Cycle (% initial dose)
Grade 1	Maintain original dose	Maintain original dose
Grade 2		
First occurrence		100% (1000 mg/m ²)
Second occurrence	Interrupt until recovery to Grade 0-1	75% (750 mg/m ²)
Third occurrence		50% (500 mg/m ²)
Fourth occurrence	Permanently discontinue the treatment	
Grade 3		
First occurrence		75% (750 mg/m ²)
Second occurrence	Interrupt until recovery to Grade 0-1	50% (500 mg/m ²)
Third occurrence	Permanently discontinue the treatment	

Grading of Adverse Drug Reactions	Modification During Treatment	Dose Modification in the Next Cycle (% initial dose)
Grade 4		
First occurrence	Permanently discontinue the treatment Or if the investigator believes that continuing treatment is beneficial to the subjects, then interrupt the treatment until the AE recovers to Grade 0-1 before resuming treatment.	50% (500 mg/m ²)

Table 8. Dose modification criteria for capecitabine

- Dose modification of oxaliplatin

Dose modification due to neurotoxicity

- ◆ For Grade 2 peripheral sensory neurotoxicity (moderate paresthesia or dysesthesia) or limited instrumental activities of daily living, oxaliplatin may be interrupted. After the toxicity recovers to grade ≤ 1 , oxaliplatin can be resumed at 75% of the initial dose. If oxaliplatin treatment has been interrupted for more than 4 weeks due to neurotoxicity (2 consecutive doses), oxaliplatin treatment should be discontinued permanently.
- ◆ For grade ≥ 3 peripheral sensory neurotoxicity (severe paresthesia or dysesthesia) or limited activities of daily living, oxaliplatin should be discontinued permanently.

Dose modification due to renal injury

- ◆ There is no need to adjust the dose of oxaliplatin for mild or moderate renal function impairment ($\text{CrCl} > 50 \text{ mL/min}$).
- ◆ For severe renal function impairment, the dose of oxaliplatin should be adjusted to 75% of the initial dose.

Dose modification due to hematologic toxicities

- ◆ For Grade 2 or 3 thrombocytopenia, the dose of oxaliplatin should be adjusted to 75% of the initial dose. For Grade 4 thrombocytopenia, the dose of oxaliplatin should be adjusted to 50% of the initial dose.
- ◆ For Grade 3 or 4 neutropenia or febrile neutropenia, the dose of oxaliplatin should be adjusted to 75% of the initial dose.

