6.2 Treatment Period/Follow-Up

The treatment period starts from the subject's first dose. The first dose of the study drugs should be given as close as possible to the time of completing the screening examinations and confirming the subjects' eligibility for the study. Each treatment cycle lasts for 21 days.

All examinations and evaluations (except for imaging evaluations) should be completed within 3 days pre-administration. There is no need to repeat the laboratory tests (hematology, urinalysis, blood biochemistry, coagulation function test, and thyroid function test) and electrocardiography on Day 1 of Cycle 1, if such tests have already been performed at the baseline within 7 days before the first dose.

- ◆ For subjects receiving the SHR-1210 + apatinib treatment for the first time, blood samples should be collected for PK and immunogenicity testing. The specific procedures can be found in the schedule of activities or section 3.1 "Pharmacokinetic and Immunogenicity Studies" in the protocol.
- ◆ The following evaluations should be completed before the drug administration in each cycle:
 - ECOG PS
 - Vital signs
 - Physical examination: Specific physical examination is performed if clinically indicated.
 - Hematology
 - Clinical chemistry
 - Coagulation function
 - 12-Lead ECG
 - Collection of AEs
 - Documentation of concomitant medications/concomitant treatments
- ◆ The following evaluations should be completed every 2 cycles prior to administration:
 - Urinalysis
 - Thyroid function
 - Fecal occult blood

- ◆ Imaging examination: Imaging examination is performed once every 2 cycles (6 weeks ± 7 days) in the first 12 months (the first 16 cycles), then once every 3 cycles (9 weeks ± 7 days). Imaging examination should be also performed if new lesions are suspected. Imaging examination should be performed when subjects withdraw from the study for any reason (the imaging examination does not need to be repeated if the time from the last examination is no more than 4 weeks). Imaging conditions should be the same as those at baseline (including slice thickness and contrast agent). The time window for imaging examination is ± 7 days. Unscheduled imaging examination may be performed if PD is suspected (for example, worsening of symptoms). The date of imaging examination is calculated by the calendar day and will not be adjusted due to dose delays.

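### The oxaliplatin neurotoxicity stop rule pairs a 4-week limit with two missed doses on a 3-weekly schedule, and its relation to the 6-week delay limit in the same section is not stated

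*Protocol*

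**What the plan says.** Three parts of the protocol bear on this point.

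- **Schedule.** Section 5.1.5 has oxaliplatin "administered on Day 1 of each treatment cycle, once every 3 weeks", and section 6.2 confirms the cycle length: "Each treatment cycle lasts for 21 days".
- **General delay rule.** Section 5.2.2 opens with a limit for toxicities of either chemotherapy drug: "The administration of capecitabine and/or oxaliplatin can be delayed for no more than 6 weeks". If the toxicity has not resolved by then, the drug is stopped, "unless the investigator considers that the subjects will benefit from the continuing treatment of the capecitabine and/or oxaliplatin".
- **Neurotoxicity rule.** Later in section 5.2.2, a Grade 2 sensory neurotoxicity may lead to a hold, with resumption at a reduced dose after recovery. The rule then reads: "If oxaliplatin treatment has been interrupted for more than 4 weeks due to neurotoxicity (2 consecutive doses), oxaliplatin treatment should be discontinued permanently". It gives no exception. Grade 3 or higher leads directly to permanent discontinuation, so the time limit matters only for Grade 2 holds.

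Neither rule says on which day an interruption starts to count, and neither refers to the other.

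**The concern.** The neurotoxicity rule is mandatory and irreversible, and it carries two criteria in one sentence: a number of weeks and a number of doses. On a 3-weekly schedule these are not the same quantity. A site that applies the weeks and a site that applies the dose count can reach opposite decisions for the same patient. A site that applies the general limit may reach a third.

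Chemotherapy in cohort 1 lasts only 4 to 6 cycles, so one or two oxaliplatin doses are a visible share of the plan, and continued exposure to a neurotoxic drug is a safety matter in itself. There is a smaller consequence for data handling. SAP section 8 lists failure to take study drug according to the protocol as a type of deviation, and a stop rule with two readings makes such deviations hard to classify in the same way at every center.

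**Working it through.** **Inputs**

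- Dosing interval: 3 weeks, or 21 days (protocol sections 5.1.5 and 6.2). Due days are therefore 1, 22, 43 and 64.
- Visit window from Cycle 2 on: Day 1 ± 3 days (Schedule of Activities, which has study treatment as a row).
- Neurotoxicity limit: more than 4 weeks (28 days), paired with two doses (section 5.2.2).
- General limit: 6 weeks (42 days), with an investigator exception (section 5.2.2).

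**Step 1: the stated pairing.** Two doses × 3 weeks = 6 weeks. Conversely, 4 weeks ÷ 3 weeks = 1.33 cycles. Two intervals make 4 weeks only on a 2-weekly schedule (2 × 2 = 4), which is not the oxaliplatin schedule here. The pairing is not reproduced as an equality.

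The next steps take a patient dosed on Day 1 whose Day 22 dose is held.

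**Step 2: count from the last dose given (Day 1).** The 28 days end on Day 1 + 28 = Day 29. Resumption on Days 30 to 42 is beyond 4 weeks, so the week limit requires a permanent stop. Only the Day 22 dose has been missed, so the dose count does not. Resumption exactly on the grid, on Day 43, meets the same conflict: 43 − 1 = 42 days since the last dose, with one dose missed.

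**Step 3: count from the missed due date (Day 22), with resumption off the grid allowed.** The 28 days end on Day 22 + 28 = Day 50. The second dose is due on Day 43 and stays within its window until Day 43 + 3 = Day 46, so it is missed only from Day 47. Resumption on Days 47 to 50 falls 25 to 28 days after the due date. The week limit allows it, but two doses have been missed, so the dose count requires a stop.

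**Step 4: count from the due date, with doses skipped whole on the grid.**

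- One skipped dose: 43 − 22 = 21 days = 3 weeks, not more than 4. Neither criterion stops treatment.
- Two skipped doses: 64 − 22 = 42 days = 6 weeks, more than 4. Both criteria stop treatment.

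Here the two criteria select the same patients.

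**Step 5: week limit against the general rule.**

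| Length of neurotoxicity interruption | Neurotoxicity rule (weeks) | General rule |
|---|---|---|
| Up to 4 weeks | No stop | Delay allowed |
| More than 4, up to 6 weeks | Permanent stop | Delay allowed |
| More than 6 weeks | Permanent stop, no exception | Stop unless the investigator expects benefit |

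The two skipped doses in Step 4 make a delay of exactly 6 weeks. The general rule permits that delay and the neurotoxicity rule bars it, so the reading that repairs the sentence internally does not remove the difference from the general limit.

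**The case against.** The best defense is that the sentence never sets 4 weeks equal to two doses. It says more than 4 weeks, and the parenthesis may simply name the number of missed doses that passes the limit. On the fixed grid that is correct (Step 4). The grid reading has support in the text: "Dose modification caused by toxicities of a single drug in the combination therapy will not affect the usage of other drugs according to the plan". If the other drugs stay on schedule, oxaliplatin doses are naturally skipped whole. This stands, and it means the sentence is ambiguous rather than wrong under every reading. A reader might infer a flat arithmetic contradiction; the documents do not support that.

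The favorable reading still needs two conditions that the protocol does not state: counting from the due date, and no resumption between grid days. It can be objected that counting from the last dose treats the ordinary 21-day interval as interruption, and that where Table 7 counts from the last dose it does so for SHR-1210 and in express words. Both remarks are fair. They make the Step 2 conflict conditional on a site taking that reading, and nothing in the oxaliplatin rule excludes it.

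On the 6-week limit, a stricter rule for one toxicity under its own subheading can naturally be read as overriding the general one, and a stricter rule without an exception is coherent. That too is plausible. But the general rule covers oxaliplatin toxicities without setting neurotoxicity apart, and no sentence gives precedence.

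**Conclusion.** The point holds as an ambiguity in a mandatory stop rule. The two criteria agree under one combination of unstated conditions. They diverge on Days 30 to 42 if the count runs from the last dose, and on Days 47 to 50 if it runs from the due date with off-grid resumption. These ranges assume 21-day cycles, a first held dose on Day 22, and the ± 3-day window applied to the second due dose. Separately, interruptions of more than 4 and up to 6 weeks are barred by one rule and allowed by the other, with precedence unstated.

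It is a minor point of consistency between centers and of safety. Sample size, alpha, power and the response thresholds are untouched. Two larger inferences are tempting and should not be drawn. One is an effect on cohort 1's response rate: nothing in the documents quantifies it, and the other drugs continue as planned. The other is a count of affected patients obtained by applying the 19% neurotoxicity figure in protocol section 1.3.1 to cohort 1. That figure is not split by grade and says nothing about held doses or their length, so it does not measure who falls in the disputed windows.

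**What to change.** Reconcile the neurotoxicity rule in section 5.2.2 with the general delay rule in the same section and with the schedule in section 5.1.5. The revised text should:

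1. express the limit in one unit, either weeks or missed 3-weekly doses;
2. state when the count starts, from the last dose given or from the missed due date, and whether oxaliplatin may resume between scheduled cycle days;
3. say which rule prevails for neurotoxicity;
4. say whether the investigator exception applies to neurotoxicity.

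The sponsor's clinical team sets the limit; none is proposed here. The cost is a short text amendment, with the ethics approval that section 11.3 requires for any revision. It adds no procedures and changes nothing in the statistical design.
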